**DATA MANAGEMENT**

**8. Data acquisition and transmission, data entry methods**

The study team will develop MOUs and Business Associate Agreements with relevant study partners for their participation in the study and HIPPA compliant exchange of information. These will formalize: (1) participation of CFD and CPD on the study advisory board and in trainings on and implementation of study procedures for first responders to solicit consent for contact from individuals following naloxone administration; (2) involvement of the IL Opioid STR project representatives in the study team and its advisory board; and (3) involvement of MAT providers in the target communities and the procedures for communicating with the study team and obtaining permission for sharing information.

All key research staff at CHS are or will be trained on the principles and process of informed consent through the Protecting Human Research Participants (PHRP) human subjects research online training program (<https://phrptraining.com>) and good clinical practice for clinical trials (<https://gcp.nidatrainig.org>) and then tested by their supervisors. All informed consents will be audiotaped for random review. If problems arise from the review, the PI and Co-PI will meet with staff to correct the problem and meet with the participant when needed to clarify any potential confusion.

The first responders will follow their standard practices for obtaining contact information from individuals following naloxone administration (i.e., name, address, phone number). For those who are alert and oriented, first responders will ask one additional question of the participants, which is whether they are willing to be contacted by someone in a few days to see how they are doing and talk about available help. If they respond affirmatively, first responders will request their signature on a form indicating their consent to share their contact information with the study investigators who will contact them, optimally within 48-72 hours. Finally, all individuals, whether or not they consent to release their information, will be provided with a brochure listing MAT providers in the local community. Research staff will pick up the release and contact forms daily from each participating firehouse and police station and document the number of people who overdosed and received naloxone and who: a) agreed, b) were not alert and/or oriented and were not asked, or c) refused. The rate of consent/refusals will be monitored against the total number of daily naloxone administrations. We will look for patterns to consent/refusal and debrief with first responders about the process. Study partners will meet every other week during the recruitment phase to monitor recruitment, discuss challenges, and develop strategies to increase recruitment, if needed. Based on the research team's success on prior studies tracking and locating participants, we expect that research staff will successfully contact approximately 75% of participants by telephone or through direct outreach. As reported in the initial focus group, we expect that almost all will currently be using opioids or heroin. Upon contact, research staff will screen individuals for eligibility based on study inclusion criteria; if eligible, they will be invited to the research office to complete the informed consent and baseline interview and will be randomized. Transportation will be provided as needed.

The Research Manager will then use gRand Urn Randomization (Version 1.10) to randomly assign 350 participants to one of the two conditions: referral to MAT control or RIMO. Urn randomization adjusts the probability of assignment to condition in ways that simultaneously minimize differences in multiple stratification variables. The base rate will be set to 50% of each condition and adjusted over time to simultaneously balance on multiple participant characteristics (gender, race, age, community) and baseline measures of key outcomes including days of opioid use in the prior 90 days, lifetime number of overdoses, high severity (3+ symptoms) on lifetime OUD, health problems, mental health symptoms, and high quarterly health care costs (more than \$7,600 dollars). The Research Manager will enter the information into the program, generate the assignment, inform participants of their group assignment, and describe the next steps. Research interviewers will be kept blind to the condition assignment for study participants.

Participants assigned to the "Referral Only" group will receive a brochure that includes a list of MAT providers in Chicago, and their location, telephone number, hours of operation, adjacent bus lines, and type of funding accepted (e.g., Medicaid). In addition, the brochure includes a range of other SUD treatment options (e.g., residential or outpatient drug-free treatment), including office-based physicians who prescribe buprenorphine or other forms of MAT. The brochure will be given to participants in both groups at the baseline assessment. Research staff will follow a script that does not include any statements regarding motivation for treatment. At present, based on our interviews with key informants and focus group with pilot study participants, there is currently no systematic method in place for referring individuals to MAT (or other SUD treatment) either from the first responders following administration of naloxone or at the EDs following their admission for opioid-related overdose. Hence, this condition represents more than the "usual care" in the community.

Participants assigned to the "RIMO" group will have a face-to-face meeting with the Linkage Manager (LM), who will engage the participants in a discussion about their willingness to go to MAT. Based on our prior trials and the pilot, we expect this meeting to take place in 1-4 working days following the OD. LM will use motivational interviewing (MI) techniques to: 1) discuss with participants the benefits of their decision to go to treatment, including activities they might enjoy as well as things they do not like about their alcohol/substance use, 2) provide personalized feedback to participants about the status of their condition based on responses to the assessment instruments, 3) help participants resolve ambivalence about their opioid use and move them toward a commitment to change by accessing treatment, 4) address existing barriers to treatment, e.g., assess Medicaid eligibility and assist with applications, problem-solve issues regarding childcare or transportation, 5) schedule a treatment appointment, 6) develop a reminder schedule for MAT appointments, and 7) problem

solve any transportation or other challenges that arise. The LM will contact participants 2-3 times/week for at least 4 weeks to ensure that participants complete detox and/or initiate and remain engaged in MAT. This includes working with the individual and the treatment provider to minimize missed doses, which can “reset” the dosing schedule. Specifically, the LM will follow-up with the treatment agency and/or participants to determine if they showed for their intake appointments and scheduled dosing for 30 days. For participants that miss a dose, the LM will contact them to discuss barriers and ways to remove them. Additionally, the LM and MAT provider will coordinate information on the participant’s barriers to treatment engagement (i.e., scheduling, transportation) and assist the participant in problem-solving solutions to support their treatment retention. During the first 30 days, the research team will provide bus cards for those in need.

For participants who refuse the referral to MAT, the LM will use motivational interviewing (MI) techniques to explore the perceived benefits and consequences of the individual’s current opioid/heroin use, as well as explore their motivation for treatment. Using empathy and reflection, the LM will explore the issues and barriers participants face when thinking about going to treatment. Using open-ended questions, the LM will explore not only reasons the individual opted out of the referral to MAT but also the potential benefits of treatment. The LM will try to develop some discrepancy between where the participant is currently and where they want to be. The LM will use the MI technique of rolling with resistance and assure the participant that the decision is up to him/her regarding treatment - empowering the participant in the decision process and encouraging “change talk”. The LM will document the various reasons that participants cite for declining the treatment referral. Learning more about the reasons for these refusals can further inform the development or refinement of strategies for improving linkages. Our experience with other similar trials indicates that many refusals are situational or temporary in nature (e.g., illness, fatigue, sick family member) and simply re-contacting the person at a later date is, in some cases, sufficient to convert a refusal. We will routinely re-contact individuals who refuse linkage to detox or MAT to ascertain if their feelings about entering treatment have changed and continue to engage with them using MI. If the individual is not interested in MAT or other types of treatment, the LM and participant will develop an alternative action plan, which may include specific behaviors and recovery activities (e.g., carry naloxone, attend self-help, get a sponsor) to reduce or stop use.

Fidelity to the RIMO procedures for engaging and linking participants to MAT and providing ongoing recovery support will be assessed in two ways. For RIMO meetings at baseline and 3, 6, and 9 months post-randomization, the LM will document the participant’s need for treatment, treatment initiation and retention. Staff will also audio record all RIMO sessions and the Linkage Supervisor will review a random sample using the Motivational Interviewing Skill Code (MISC) to measure key constructs like “change talk” that are associated with positive outcomes.

To measure change, research staff at baseline, 3, 6, and 9 months post enrollment will interview patients using the 25-minute Global Appraisal of Individual Needs Quick Version 3 (GAIN-Q3). The GAIN-Q3 includes 4-6 symptom count screeners that are correlated .9 or more with the 11 to 43-symptom version in the full GAIN. It also has cut points with excellent (~90%) sensitivity, specificity, and area under the curve (AUC) relative to the full GAIN in 9 problem areas related to substance use disorders, physical health, internalizing and externalizing mental health disorders, as well as school, work, stress, HIV risk behaviors/victimization, and crime/violence. The days of use measures have been validated against the Timeline Follow-back, collateral reports, and urine and saliva tests. The GAIN-Q3 also includes summary measures for health care utilization, functional impairment, quality of life, and life satisfaction. The GAIN-Q3 includes the behavioral health screener and health care utilization measures that have been recommended by NIH’s Phenx common data elements as two of the most reliable, valid, efficient, and inexpensive tools in the field. At each follow-up, the Q3 follow-up will be supplemented with a) a section on overdose and naloxone experiences, and b) symptom counts from the OUD scale. Data will be collected via a cloud-based computer program that controls ranges and skip outs and identifies major inconsistencies for interviewers. Drs. [name] and [name] will train and supervise research staff. All interviews will be digitally recorded and a random sample reviewed for quality assurance. Our QA process has previously produced consistently good psychometrics across staff, sites, and mode (in person vs. by phone). The GAIN manual, norms, and a list of over 400 GAIN-related publications are available at [www.gaincc.org](http://www.gaincc.org).

Wherever possible, the interviews with the GAIN-Q3 and other supplements will be done via computer assisted interview using chestnut’s existing HIPAA and HITECH compliant cloud-based software (see [www.gaincc.org](http://www.gaincc.org)). In use by over 3,500 agencies in all 50 states, this software incorporates skips, range and error checking in real time. It helps interviewers to go through complex question matrices of questions with fewer errors, leaves less missing data, and provides an immediate validity report to reduce inconsistencies

across multiple items. In the event that the data is collected on paper and pencil, this same software can be used for data entry.

The team will implement [name] follow-up procedures which have reliably produced over 90% follow-up rates across studies involving over 70,000 patients regardless of age (adolescents, young adults, adults) or population (homeless, justice involved, undocumented) over follow-up periods ranging from 3 months to 19 years. This includes follow-up interviews with 90% of the adolescents in the team's prior studies from up to 42 months intake. Steps include: a) contacting participants within 24-48 hours to collect additional locator information and mailing a schedule card for the next interview; b) receipting information in an MIS; c) assigning each case to a follow-up case tracker; d) verifying locator data; e) conducting outreach for unverified cases and discussing them at weekly meetings; f) mailing thank-you cards to participants and collaterals; g) scheduling follow-up appointments; h) mailing 3 and 6 week post-enrollment flyers; i) implementing returned-mail procedures; j) calling participants 6 weeks before appointment to confirm date and location (phone vs. research office); k) conducting outreach for unconfirmed cases and reviewing them at weekly meetings; l) completing follow-up interviews and scheduling next appointments; and m) implementing a no-show protocol. Progress will be monitored with daily management reports.

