## **2. Primary and secondary objectives and outcome measures**

The primary outcome measure for the study is the GAIN-Quick Version 3 (GAIN-Q3). The GAIN-Q3 includes 4-6 symptom count screeners that are correlated .9 or more with the 11 to 43-symptom version in the full GAIN. It also has cut points with excellent (~90%) sensitivity, specificity, and area under the curve (AUC) relative to the full GAIN in 9 problem areas related to substance use disorders, physical health, internalizing and externalizing mental health disorders, as well as school, work, stress, HIV risk behaviors/victimization, and crime/violence. The days of use measures have been validated against the Timeline Follow-back, collateral reports, and urine and saliva tests. The GAIN-Q3 also includes summary measures for health care utilization, functional impairment, quality of life, and life satisfaction. The GAIN-Q3 includes the behavioral health screener and health care utilization measures that have been recommended by NIH's Phenx common data elements as two of the most reliable, valid, efficient, and inexpensive tools in the field. At each follow-up, the Q3 follow-up will be supplemented with a) a section on overdose and naloxone experiences, and b)

symptom counts from the OUD scale. Table 2.1 crosswalks the key independent measures and secondary outcomes from the hypotheses to their definitions, reliability, data sources, and the specific aims they address.

Table 2.1. Crosswalk of Variables, Definition, and Aims	H1	H2	H3
Experimental Assignment: Based on computer-generated urn randomization, participants will be assigned to the referral only control group or the experimental RIMO condition.	R	R	R
MAT Time to Initiation: Days from index naloxone administration to the initiation of any kind of MAT, from treatment records.	O		
Length of Staying on Medication: Days between MAT initiation and discharge, from treatment records.	O		
MAT Days: Total days of MAT over 9 months from GAIN-Q3 and treatment records.	O	M	M
Time to Relapse: Days from randomization to next subsequent use of opioids or heroin based on GAIN Q3 follow-up interviews and urine tests.		O	
Opioid Days of Use: Days of opioids and/or heroin use summed over the GAIN-Q3 follow-up interviews.		O	M
Opioid Overdose: Number of opioid-related overdose[s] summed over the GAIN-Q3 follow-up interviews.		O	

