## **10. Statistical analysis plan**

Missing data. Participants will complete their baseline interview prior to randomization. Based on prior studies conducted by the applicants, it is expected that approximately 90% or more of the 3, 6, and 9-month post-randomization interviews will be completed. Among these completed interviews, prior studies conducted by the team indicate that less than 1% will have additional missing data on any of the core items required to test the study hypotheses. Multiple imputations will be used to replace the small amounts of missing data to allow the least biased estimate for each analysis. To further reduce potential bias, analyses will be rechecked by running them without missing data. If there are any clinically significant differences ( $d > |.2|$ ), a general latent variable framework will be used to analyze non-ignorable or systematic missing data that tests whether missing data is qualitatively different by condition.

Survival Analysis for Time to MAT Initiation and Time on Medication (Aim 1). The primary outcome is the days from randomization until the initiation of any kind of MAT. Relative to the referral only control group, the direct effects of RIMO on reducing the days from randomization to initiation of any MAT (H1a) and increasing the days on medication after initiation (H1b) will be evaluated with a Cox Regression model using IBM SPSS version 24 with random assignment to RIMO as the main predictor, as the investigators have done in earlier experiments. It will be examined after the point of randomization and after each follow-up interview. Survival analysis incorporates information about censorship (e.g., death, people who were not admitted to MAT within 9 months) and can incorporate covariates if needed. The output includes a case summary (e.g., missing data, other problems, descriptive statistics) and an evaluation of each term (e.g., beta, its standard error, Wald, its probability, the odds ratio, the 95% confidence interval for the odds ratio). The beta can also be converted to a Cohen's effect size *d*. All analyses will use an intent-to-treat approach (i.e., participants are analyzed as assigned regardless of their actual level of participation in RIMO). We will also conduct a secondary analysis of the time to MAT initiation after each RIMO checkup to understand the pattern over time as we have done with earlier experiments.

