## **12. Procedures to guarantee the accuracy and completeness of the dataset**

Drs. [name] and [name] will train and supervise research staff. Interviews are checked for completeness and relative to urine tests at office visits. All interviews will be digitally recorded and a random sample reviewed for quality assurance. Our QA process has previously produced consistently good psychometrics across staff, sites, and mode (in person vs. by phone). The GAIN electronic interview conducts range checks, makes simple and complex skips, and allows immediate consistency checks. If an interview needs to be done with paper and pencil (e.g., jail, hospital), the interviewer will field edit it followed by a second edit to verify that key fields are complete, provide feedback and/or get clarification of questions, and mark any missing/bad data. The Research Manager will review inconsistent or missing data with the interviewers. When the data are keyed, the computer system will again check for range and consistency across multiple items. Weekly management reports will be used to monitor performance and error reports will be reviewed weekly until there are no major problems (or when there is new staff), then monthly thereafter. All GAIN data will be checked for unexpected patterns of increased or decreased activity.

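### The Research Manager, who generates and announces each assignment, also reviews inconsistent or missing interview data with the blinded interviewers, and no safeguard is stated

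*Combined protocol and SAP*

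**What the plan says.** Section 8 (Data acquisition and transmission, data entry methods) describes how assignments are made: "The Research Manager will enter the information into the program, generate the assignment, inform participants of their group assignment, and describe the next steps". The next sentence gives the plan's blinding commitment: "Research interviewers will be kept blind to the condition assignment for study participants". It covers interviewers only. Nothing similar is promised for the Research Manager or for those who edit data.

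Section 12 describes checking of the interview data: "The Research Manager will review inconsistent or missing data with the interviewers". The same sentence stands in Section 1, under Data Editing and Quality Assurance. In both places it follows the handling of paper interviews, for which "the interviewer will field edit it followed by a second edit to verify that key fields are complete"; the second editor is not named. Section 12 also says: "Interviews are checked for completeness and relative to urine tests at office visits". It does not say who makes that comparison.

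**The concern.** The plan chose interviewer blinding as a protection for its interview outcomes. Participants and Linkage Managers cannot be blind to arm, so that protection is worth keeping intact. As written, the person who knows every participant's arm sits down with the blinded interviewers to go over doubtful answers.

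This opens two routes to bias. Knowledge of arm could influence how a doubtful answer is settled. Arm could also become known to an interviewer who will see the same participant at a later wave. Days of MAT and days of opioid use are mediators in Aims 2 and 3 as well as outcomes, so any distortion would carry into the indirect effects.

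**Working it through.** The plan gives no figure for this risk, so there is none to reproduce. The check is mainly a comparison of roles, with a short count to bound the size.

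**1. Roles**

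| Task | Who | Where |
|---|---|---|
| Runs the urn program and tells participants their arm | Research Manager | Section 8 |
| Kept blind | Research interviewers | Section 8 |
| Goes over inconsistent or missing data with the interviewers | Research Manager | Sections 1 and 12 |

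**2. Stated safeguards.** No section masks the arm at that review, bars discussion of arm, names another reviewer after randomization, or requires a log of edits. The de-identification in Sections 9 and 19 applies to data sets prepared for analysis, not to field editing.

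**3. Outcomes exposed.** Table 2.1 lists 11 outcomes.
- Not exposed through interview answers (3): time to MAT initiation ("Days from index naloxone administration to the initiation of any kind of MAT, from treatment records"), length of staying on medication (treatment records), and opioid-related fatality (death records).
- Exposed (6): opioid days ("Days of opioids and/or heroin use summed over the GAIN-Q3 follow-up interviews"), overdoses, OUD symptoms, physical health, mental health and cost.
- Exposed in part (2): MAT days (interviews and treatment records) and time to relapse (interviews and urine tests).

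Baseline answers are outside the concern, because "Participants will complete their baseline interview prior to randomization".

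**4. Number of interviews.** Follow-up interviews = N × waves × completion, with N = 350 and 3 waves.
- At 90% completion (Section 10): 350 × 3 × 0.90 = 945.
- At 94% completion (Section 4): 350 × 3 × 0.94 = 987.

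Section 10 expects less than 1% of completed interviews to lack a core item: 0.01 × 945 = 9.45 and 0.01 × 987 = 9.87, so fewer than about 10. The rate of inconsistent answers is not given.

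**5. What it would take to matter.** This is an illustration under an assumption that is not in the documents. Suppose a share q of one arm's interviews is each shifted by 1 SD in the same direction, and ignore any change in the SD. The bias in d is then about q × 1 = q.

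| q | Bias in d |
|---|---|
| 1% | 0.01 |
| 5% | 0.05 |
| 10% | 0.10 |
| 20% | 0.20 |

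Section 4 gives d = 0.2 as the detectable effect for the other direct effects. One arm has about 945/2 = 472.5 to 987/2 = 493.5 follow-up interviews. A bias of 0.2 would therefore need about 0.20 × 472.5 = 95 to 0.20 × 493.5 = 99 of them shifted one way. If all the interviews with missing core items fell in one arm and shifted together, the bias would stay below about 9.87/493.5 = 0.02.

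**The case against.** A reader might infer that the blind is broken and that the Research Manager decides the disputed answers. The documents support neither. They state that interviewers will be kept blind, and nowhere say that arm is disclosed or needed at the review. They speak of a review with the interviewers, not of who makes the final change. Nor do they say that the Research Manager settles conflicts between self-report and urine.

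A reader might also infer that every follow-up interview passes through this step. The review sentence comes after the paper-interview edits and before keying, so it may belong mainly to that workflow. Computer-assisted interviews, the default, are checked for range and consistency as they are taken. Even on the broad reading, only inconsistent or missing answers are reviewed.

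Nor is interviewer blinding the only protection. Urine tests, treatment records and software checks are planned. All interviews are recorded, and Section 25 has every recording reviewed until a staff member is certified, then two per person per month. An altered answer could be checked against its recording.

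All of this stands, and it limits the point. It does not remove it: none of these measures keeps the arm from the person conducting the review, and the overlap of roles is explicit.

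**Conclusion.** The overlap is real and no safeguard is stated. It puts at risk, but does not demonstrably break, the interviewer blind and arm-neutral editing for the eight interview-based outcomes at 3, 6 and 9 months, two of them only in part. It does not reach baseline data or time to MAT initiation, which Sections 4 and 10 name as the primary outcome. Section 20 instead calls a substance frequency scale primary and bases the stopping rule on it. If that scale comes from the interviews, which the documents do not state, it is exposed too.

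The size is unknown. Missing core items alone could hardly matter. Review of inconsistent answers would matter only if it were frequent and its edits leaned one way, and the plan gives no rate from which to judge. The conclusion rests on the same role-holder doing both tasks throughout, as the text reads. It is a cheap improvement to a safeguard that the plan already claims, not a threat to the primary comparison.

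**What to change.** In Section 1 (Data Editing and Quality Assurance) and Section 12:
- Assign review of inconsistent or missing post-randomization data to existing data staff who have no access to assignments and who work from listings without arm. Staff who prepare the outcome comparisons for the annual monitoring report would not qualify if they hold the assignments.
- State that no one with access to assignments takes part in outcome queries.
- Log each edit with editor, date, and value before and after. The number of edits by arm can then be reported at the end.

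Leave the urn program where it is, away from linkage staff. Moving it to them would put allocation in the hands of those who deliver RIMO and weaken concealment.

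The cost is a handover between existing staff and a short delay in settling queries. Sample size, power and participant procedures do not change.
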